Recent evidence suggests that visual field loss is associated with neuroanatomical changes in the brain, offering some interesting insights on vision-related brain plasticity. For instance, peripheral vision loss was associated with cortical thickness (CT) decrease in dorsal area V3d, early visual cortex (V1&2) and ventral area V4, while central vision loss was associated with CT decrease in V3d and V3A⁵⁴. The mechanisms responsible for these changes, however, remain unclear. Prins et al.⁵⁵ showed that there was a decrease in gray matter volume in the bilateral superior lateral occipital cortices in a group of monocular blind patients when compared to a group of healthy controls, but that there were no volumetric differences in their visual cortex. These results are consistent with a functional deprivation hypothesis, rather than a trans-synaptic degeneration hypothesis, since the superior lateral occipital cortices play an important role in depth perception, and early visual cortex was spared⁵⁵. Another study compared CT in 10 patients with macular degeneration (MD) to healthy controls⁵⁶. Despite the small sample size, results indicated that MD participants had significantly reduced CT in centrally-responsive primary visual cortex, but interestingly that they had increased CT in peripherally-responsive primary visual cortex. This suggests that compensatory recruitment of spared peripheral vision may induce cortical thickening in specific areas of the visual cortex⁵⁶, a finding that would support the idea of improved function (e.g., reading) using the peripheral retina for reading after the development of AMD. Taken together, these results highlight the potentially important mechanisms of brain plasticity following visual loss, but they need to be replicated using a larger sample. Importantly, these results also open the crucial question of whether vision rehabilitation therapy may induce even more important changes in brain plasticity. To our knowledge, this question has never been addressed before. Therefore, the general **neuroimaging objectives** of this project will be 1) to investigate if visual impairment is associated with reduced cortical thickness in specific cortical areas at baseline (cross-sectional portion), and if vision rehabilitation will result in changes in cortical thickness after 12 months (longitudinal portion).

Does Reduced Reading Effort allow for Increased Reading Activity, Leading to Improved memory/cognition?

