- There will be reduced CT in the visual cortex in the low vision groups compared to matched controls at baseline
- Reading rehabilitation results in increased CT in the low vision groups, but not in the control group after 12 months.

Ethics Approval has been obtained through the *Comité d'éthique de la recherche* of the *Centre de recherche interdisciplinaire en readaptation du Montreal metropolitan (CRIR#1284-1217)* which is responsible for research protocols involving recruitment from the clinical partners (local sensory rehabilitation centres) within this study: the *CRIR/Centre de réadaptation MAB-Mackay du CIUSSS du Centre-Ouest-de-l'Île-de-Montréal*, and the *CRIR/Institut Nazareth et Louis-Braille du CISSS de la Montérégie-Centre* (see attached letters of support). Additional approvals and modifications (MRI component) will be obtained through the university affiliations of the team members.

Study Design: We will employ a quasi-experimental approach (non-randomized, pre-post intervention study)⁶³, an approach frequently used during the evaluation of health interventions⁶⁴. Specifically, a 3x3 design (3 groups x 3 time points) will allow us to examine whether cognitive performance will change before and after 6 and 12 months of a low vision reading intervention, when comparing LV and dual sensory impaired (DSI) patients to age-matched controls with age-normal vision and hearing⁶⁵. Participants will be audio-recorded throughout several of the tasks to ensure the highest level of precision when inputting and analysing data, and to help reduce the overall testing time. All aspects of the study design and data analysis will be submitted as a stage 1 pre-registered report.

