Clinical Variables: As part of any low vision exam, the eye care professionals within each of the rehabilitation centres record key variables in the patients' charts that will be available for extraction by the research team as part of their study consent. They include, but are not limited to: diagnoses (ocular and otherwise), monocular and binocular visual acuity (distance and near), contrast sensitivity, visual field diameter, type and duration of rehabilitation services provided (e.g., computer rehab, orientation & mobility services), type of assistive devices that were prescribed and provided (please note that these devices are free loans for life through Quebec Health Insurance/RAMQ; therefore, income is not a barrier to device use). The file contains information about the type and intensity of vision rehabilitation strategies that were implemented and trained (e.g., provision of improved lighting, strategies to read while placing materials on reading stands at the appropriate distance). In addition, the file contains basic demographic information (e.g., gender, age, living situation). These clinical variables will be available to the research team for the purpose of comparison, as well as statistical control and analysis.

MRI Acquisition – Subsample of 45 Participants (15 VI, 15 DSI, 15 control)

Imaging data will be acquired using a 3T Siemens Prisma fit MR scanner (Siemens, Erlangen, Germany) at the *Unité de neuroimagerie fonctionnelle of the Institut universitaire de gériatrie de Montréal*. High-resolution T1-weighted images will be acquired using a magnetization-prepared rapid acquisition with gradient-echo (MPRAGE) sequence, with the following parameters: TR=2.4 s,

TE=2.33 ms, TI=979 ms, flip angle=9 degrees, FOV=230x230, voxel size: 0.8 mm x 0.8 mm x 0.8 mm. Additional FLAIR, resting-state and DTI sequences will also be included as exploratory measures. Total acquisition time will last < 30 minutes plus 15 min instruction and preparation.

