MRI image analysis: Cortical reconstruction will be performed using FreeSurfer (version 6.0.0)^{88,89}. The following method uses both intensity and continuity information from the entire three-dimensional magnetic resonance volume in segmentation and deformation procedures to produce representations of cortical thickness, calculated as the closest distance from the grey matter-white matter boundary to the grey-CSF boundary at each vertex on the tessellated surface⁹⁰. Maps of cortical volume and cortical surface area will also be generated for exploratory purposes. Briefly, this processing includes motion correction⁹¹, removal of non-brain tissue using a hybrid watershed/surface deformation procedure⁹², automated Talairach transformation, and segmentation of the subcortical white matter and deep grey matter volumetric structures^{93,94}. This is followed by intensity normalization⁹⁵, tessellation of the grey matter-white matter boundary, automated topology correction^{96,97}, and surface deformation following intensity gradients to optimally place the grey matter-white matter and grey matter-CSF borders at the location where the greatest shift in intensity defines the transition to the other tissue class^{89,90,98}. Once the cortical models are complete, a number of deformable procedures can be performed for further data processing and analysis including surface inflation⁹⁹, registration to a spherical atlas, which is based on individual cortical folding patterns to match cortical geometry across subjects, parcellation of the cerebral cortex into units with respect to gyral and sulcal structure^{100,101}, and creation of surface-based maps of CT. The maps produced are not restricted to the voxel resolution of the original data, thus are capable of detecting submillimeter differences between groups. Procedures for the measurement of cortical thickness have been validated against histological analysis¹⁰² and manual measurements^{103,104}. The maps are created using spatial intensity gradients across tissue classes and are therefore not simply reliant on absolute signal intensity. Cortical maps will be smoothed using a 20-mm FWHM Gaussian smoothing kernel. Images will be inspected and pial and white matter surface errors will be manually corrected. Figures will be created using Qdec included in the FreeSurfer distribution.

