inferior occipital gyrus, the middle occipital gyrus (and sulcus), the superior occipital gyrus, the cuneus, the lingual gyrus, the occipital pole, and the calcarine sulcus. CT will be investigated more specifically inside visual areas, namely V1 (BA17) – primary visual area, V2 (BA18) – secondary visual area, and V5/MT – visual area, middle temporal, by using an atlas from the Martinos Center for Biomedical Imaging (US) and the Institute of Neurosciences and Biophysics (Germany) (<http://surfer.nmr.mgh.harvard.edu/fswiki/BrodmannAreaMaps>). In order to examine if vision rehabilitation will result in changes in CT, we will examine by calculating percentage difference in extracted CT values for each of the above-mentioned visual regions pre- and post- reading rehabilitation. Differences between groups or between regions pre- and post-intervention will be considered significant at $p < 0.05$ after correction using false discovery rate.

Limitations & Mitigation Strategies:

Given the logistics of having the reading intervention delivered through services that are regulated by the Quebec Ministry of Health, we place our trust in the quality of rehabilitation service delivery without being able to control this aspect of the study; however, we believe that this trust is well deserved, given the quality and type of care provided in Quebec¹¹⁴⁻¹¹⁶. It is likely that a certain number of participants will self-select not to complete the 1-year follow-up or to abandon parts of the recommended intervention tools and techniques. Therefore, we will examine differences in participant characteristics and consider intent-to-treat within the statistical analyses. We expect certain variability in the cognitive status of our participants, as there are no cognitive exclusion criteria. This pragmatic approach to recruitment is chosen intentionally as we speculate that the beneficial effect of reading rehabilitation may become apparent at different levels of magnitude, depending on the cognitive starting point; however, this remains speculation at this point. Our statistical analyses will need to consider this additional source of variability.

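### Manual surface edits are planned with no masking to group or time point, and only single-scan reconstruction is described for a pre/post cortical thickness change

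*Combined protocol and SAP*

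**What the plan says.** All references are to the combined protocol and SAP.

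- **MRI image analysis** names FreeSurfer 6.0.0 and runs through motion correction, tissue segmentation, surface placement by intensity gradients, atlas registration across subjects and smoothing. It defines thickness as the distance between the grey-white boundary and the grey-CSF boundary. It then adds: "Images will be inspected and pial and white matter surface errors will be manually corrected".
- **Statistical Analysis - Cortical thickness** measures change by "calculating percentage difference in extracted CT values for each of the above-mentioned visual regions pre- and post- reading rehabilitation". Differences between groups or regions are tested at 0.05 "after correction using false discovery rate".
- **Structure-Function Relationships** sets the longitudinal objective: "if vision rehabilitation will result in changes in cortical thickness after 12 months".
- **Hypotheses** gives the direction: "Reading rehabilitation results in increased CT in the low vision groups, but not in the control group after 12 months". It also predicts thinner visual cortex in the low vision groups at baseline.
- **MRI Acquisition** fixes the sub-study at 45 people, 15 in each of the vision-impaired, dual-impaired and control groups. **Study Design** calls the study a "non-randomized, pre-post intervention study".

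No section says whether editors know group or time point, gives rules or a reliability check for edits, or says whether a participant's two scans are processed jointly or separately.

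**The concern.** Manual editing acts directly on the measured quantity, because the edited surfaces are the two boundaries whose separation is the thickness. An editor who knows the group, or which scan came first, also knows what the hypotheses predict. Small, unintended differences in how boundaries are corrected could then look like thinning at baseline or thickening after rehabilitation. With no randomisation and with controls as the only outside reference for change, such a difference would be hard to separate from a real effect. Neither covariate adjustment nor false discovery rate correction removes it.

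The second issue is precision. If each scan is reconstructed on its own, the placement errors of both scans enter the percentage difference. With 15 people per group there is little room for extra noise, and the plan describes no step that links a person's two scans.

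**Working it through.** **The plan's own figure.** The documents give no power figure, thickness SD or test-retest error for the imaging sub-study. The only power-based figure is n = 141 for the main study. It reproduces (power 0.952) as a group-by-time interaction with effect size f = 0.15, three groups, three time points and alpha 0.05, if a correlation of 0.5 and sphericity are assumed. It has no bearing on imaging. Everything below is illustration on assumed values.

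**How much slack the sub-study has.** Two-sided two-sample t test, alpha 0.05 unadjusted, 80% power. The detectable standardised difference in change is:
- 15 v 15: 1.06
- 30 v 15 (both low vision groups against controls): 0.91

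The Sample Size section expects about 10% attrition at each time point. Over two follow-ups, 15 × 0.9 × 0.9 ≈ 12 per group. The figures become 1.20 (12 v 12) and 1.02 (24 v 12).

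**Bias.** Suppose there is no true effect, but editing shifts the group difference in change by b SDs of change. The chance of a significant result at a nominal 5% is:

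| b | 15 v 15 | 30 v 15 |
|---|---|---|
| 0.1 | 5.8% | 6.1% |
| 0.25 | 10.1% | 12.1% |
| 0.5 | 26.2% | 34.0% |

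To give a physical scale, take a boundary shift of 5% of the 0.8 mm voxel, which is 0.04 mm, on cortex assumed to be 1.8 to 2.5 mm thick. That is 0.04/2.5 = 1.6% to 0.04/1.8 = 2.2% if the whole region moved. If only 10% of the region were edited, it would be about 0.16% to 0.22%.

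**Noise.** Assume a true-change SD of 1% and a per-scan error SD of e%, independent between scans.
- SD of change = √(1² + 2e²). For e = 1, 2, 3 this is 1.73, 3.00, 4.36.
- 15 v 15: standard error = SD × √(2/15); times t(28) = 2.05, the 95% half-widths are 1.3, 2.2, 3.3 percentage points.
- 30 v 15: standard error = SD × √(1/30 + 1/15); the half-widths are 1.1, 1.9, 2.8.
- If errors in a person's two scans correlate at 0.5, SD = √(1 + e²) = 1.41, 2.24, 3.16, and the 15 v 15 half-widths are 1.1, 1.7, 2.4.
- If joint processing halved e (an assumption, not a known gain), SD = 1.22, 1.73, 2.35, and the 15 v 15 half-widths are 0.9, 1.3, 1.8.

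These half-widths ignore dropout and multiplicity over regions, both of which would widen them.

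**The case against.** The strongest reply is that silence is not a plan to do the wrong thing. A reader might infer that the protocol prescribes open editing and separate reconstruction. It prescribes neither. The pipeline is introduced as a brief summary, and a percentage difference of extracted values fits joint or separate processing. This stands: separate reconstruction is a fair inference from a detailed account that contains only single-scan steps, but it is still an inference.

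A reader might also infer that the endpoint is shown to carry bias or avoidable noise of a known size. The documents do not support that either. They give no expected change in thickness, no scan error and no evidence on what longitudinal processing gains. The 0.04 mm shift and the halved error are unsourced. Edits correct errors after automated placement, so a shift of a whole region is an extreme case. Error common to both scans largely cancels in the difference, and biasing the group contrast in change requires edits that differ by group and time point together. Random error alone costs precision and does not create a systematic effect. The section also says that the maps are not limited to voxel resolution, so voxel size alone does not show that a change is undetectable.

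Finally, Study Design promises a stage 1 pre-registered report, where such details could be settled. That is a reason to settle them there, but it does not show that they are settled. A team that edited unmasked and processed each scan separately would comply with the present text.

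**Conclusion.** The point holds as a gap in the measurement procedure. The plan has people edit the surfaces that define the imaging outcome, states no masking, and describes nothing to limit independent segmentation error in the change score. It therefore permits operator bias in both the baseline and the 12-month comparison, in a non-randomised sub-study with 15 per group and directional hypotheses. That bias has occurred or will occur is not shown, and the size of bias or noise cannot be derived from the documents. The figures above show only that modest shifts or errors would matter at this sample size.

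The scope is the 45-person MRI sub-study; the cognitive outcomes are unaffected. This is a cheap improvement to a stated objective and hypothesis.

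**What to change.** 1. In MRI image analysis, give every scan a random code (at most 45 × 2 = 90), held by an existing team member who does not edit. State that all inspections and edits are made without knowledge of group or time point.
2. For the 12-month analysis, process each participant's two scans jointly with a within-subject longitudinal method, for example FreeSurfer's longitudinal stream. State in Statistical Analysis - Cortical thickness that the regional values for the percentage difference come from that output.
3. State that single-scan values are used only for the baseline cross-sectional comparison.
4. Carry the same wording into the stage 1 report.

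The cost is protocol wording, the coding of the scans, and some extra processing and quality-check time per pair. No new scans are needed. One side effect needs care: each person will have two baseline thickness values, and each must be tied to its own analysis in advance.

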Pilot data from our currently funded FRQS project focusing on cognition and AMD indicate correlations between sensory and cognitive variables in the expected directions insofar as individuals with faster reading speeds demonstrated better scores on the Montreal Cognitive Assessment^{57,58}. Given the information reviewed above, the logical direction for our investigation into the functional connection between LV and cognition is to examine the possible effects of reading rehabilitation on the cognitive abilities of LV patients over time. In order to dis-entangle the effects of visual and cognitive impairments in older adults, members of this research team have adapted cognitive tests so they can be administered to individuals with low vision^{59,60}. In parallel, we are also in the process of developing a vision-screening test that can be administered to individuals with various levels of cognitive impairment^{61,62}. This investigation will guide our future research efforts into the improvement of service provision in LV rehabilitation for the purpose of increasing the independence and health of older adults living with LV.

[figure not shown]
The objectives are to:

- Evaluate cognitive functioning and memory before, and 6 and 12 months after low vision reading rehabilitation using magnification in AMD patients, compared to those with dual (vision and hearing) impairments, and age-matched controls
- Correlate participant characteristics with all cognitive outcome variables in order to identify potential mediators, moderators or confounders

Hypotheses:

- Measures of reading effort (self-report and objective reading speed) will be statistically significantly reduced after participants have received strategies and tools to facilitate reading.
- Measures of reading behaviour will be negatively correlated with measures of reading effort (e.g., participants who report less effort will read a greater amount, more frequently and for longer)
- Individuals who demonstrate reduced reading effort and improved reading behaviour will demonstrate improved scores on cognitive tests after 6 months of having received rehabilitation strategies and tools, compared to those whose reading effort remains high or whose reading behaviour remains unchanged. These beneficial effects will be maintained after 12 months.
- Reading measures correlate with cortical thickness (CT) in the visual cortex;

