Sample Size: Effect sizes in vision rehabilitation in the past have ranged from approximately Cohen's $d = .20$ to 2.5 ³⁸. Since there are no existing effect size estimates for cognitive ability in the context of low vision rehabilitation, we are applying these values as a guide line: Using an average value of $d = 1.0$, and converting this value into variance accounted for ($r^2 = .20$ ¹⁰⁵), we can estimate a required sample size. Using a 3x3 (group x time point) within-between design for Analysis of Variance, power analysis using gPower¹⁰⁶ indicates that a sample size of $n = 141$ allows us to detect small effect sizes of .15 or greater, with an alpha of 0.05 and a desired power of .95. We expected an attrition rate of around 10% at each time point, given our previous research with older visually impaired adults^{107,108}. Therefore, a sample of $n = 200$ (to yield 150 patients, 50 controls) should be sufficient for our protocol. This goal is feasible given an average of 3000 new referrals to rehabilitation in Montreal per year.

Data Collection

Time 1 – Pre-Reading Rehabilitation: Participants will complete the questionnaires, hearing, reading and cognitive assessment components between their initial global intake exam and their first rehabilitation appointment. This period can span anywhere around 3 months, depending on waiting lists, and we will track whether any substantial changes in health occurred during this period that could influence eligibility or data collection.

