Time 2 – 6-Months and Time 3 – 12-Months Follow-Up: Six and 12 months after the initial rehabilitation appointment, the research assistant will meet with each participant (at home or in the lab, according to their preference) in order to repeat the experimental protocol, and all reading, cognitive and hearing measures will be administered each time. Throughout the period of the protocol, data from the rehabilitation chart will be extracted as it becomes available, with the final data collection concluding after the 12-month follow-up.

Statistical Analysis – Functional measures: To analyze these data, we will examine change in cognitive test scores from baseline over time using mixed-effects regression models, adjusting for level of vision and hearing impairment as fixed or random effects, and compare across sensory group (VI/DSI/Control). The analyses will include consideration of potential moderators or confounders (i.e., gender, age, education). In addition, we will calculate effect sizes, confidence intervals and Bayes Factors for main effects, interactions, and all post-hoc analysis.

When reflecting on the question of a control group we further consulted with the rehabilitation centres and discussed recruitment approaches and limitations; however, for practical and ethical reasons we are not able to withhold rehabilitation services from a possible comparison group, and waiting times are too varied across the centers and seasons of the year to allow for a waiting-list control group. As a result, we are proposing a quasi-experimental repeated-measures design with the intent to let the participants act as their own comparison across time points.

In addition, the data allow us to follow potential **exploratory avenues of analysis:**

- 1) If the recruited participants naturally divide into individuals whose reading effort was reduced and their reading activity has increased, versus those where we do not observe a change in reading behaviour, we can compare these two groups directly (e.g., while still considering their hearing status, or their gender)

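### The cognitive tests have no primary outcome and no error control; separately, the sample-size section states its sensitivity of .15 without metric or inputs

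*Combined protocol and SAP*

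**What the plan says.** **Cognitive tests.** Cognitive Outcome Measures lists three domains and four tests: the RAVLT, Letter Number Sequencing, an auditory listening span and a choice reaction time task. The adapted MoCA appears under the same heading but is described as supplementary information. No test is ranked first. For the RAVLT, the section does not say which score will be analysed.

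**Analysis.** Statistical Analysis – Functional measures says "we will examine change in cognitive test scores from baseline over time using mixed-effects regression models". It promises effect sizes, confidence intervals and Bayes Factors for main effects, interactions and post-hoc analyses. It gives no multiplicity rule. Statistical Analysis – Cortical thickness does: Monte-Carlo cluster significance for the vertex-wise maps, and false discovery rate for the regional comparisons.

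**Status of one comparison.** The third item under Hypotheses predicts better cognitive scores at 6 months in people whose reading improves, "compared to those whose reading effort remains high or whose reading behaviour remains unchanged", and adds "These beneficial effects will be maintained after 12 months". The functional analysis section lists the same comparison among "exploratory avenues of analysis" and makes it conditional: "If the recruited participants naturally divide into individuals whose reading effort was reduced and their reading activity has increased".

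**Sample size.** The section cites Cohen's d from .20 to 2.5 and takes d = 1.0, "converting this value into variance accounted for" (r² = .20). It then turns to the power software, "Using a 3x3 (group x time point) within-between design for Analysis of Variance", and reports that n = 141 "allows us to detect small effect sizes of .15 or greater, with an alpha of 0.05 and a desired power of .95".

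**The concern.** The title question is whether reading rehabilitation improves cognition. If four or five tests are each judged at 0.05 with none named in advance, one favourable result can be presented as the answer at an error rate it does not have. The imaging sub-study is protected against this and the main question is not. The differing status of the improver comparison adds a further route by which the headline result could be chosen after the data are seen.

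The sample-size sentence raises a smaller issue. The figure .15 has no metric, and the only metrics the section names are d and r². A reader may take .15 as a standardised mean difference and so credit the study with more sensitivity than was calculated.

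**Working it through.** **1. Family error across the cognitive tests.** Inputs: four tests, or five with the MoCA (Cognitive Outcome Measures); 0.05 per test; one test per outcome.

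- Independent tests: 1 − 0.95⁴ = 0.185; 1 − 0.95⁵ = 0.226.
- Two-sided tests correlated 0.5, by simulation: about 0.16 for four and 0.18 for five.

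The correlation is an assumption. The figures count one test per outcome, whereas the plan also foresees main effects, interactions and post-hoc tests.

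**2. Reproducing n = 141.** For the group-by-time interaction with 3 groups and 3 visits:

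λ = f² × N × 3 × ε / (1 − ρ), df₁ = 4ε, df₂ = 2(N − 3)ε.

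With f = .15, ρ = 0.5 and ε = 1:

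- N = 141: λ = 0.0225 × 141 × 3 / 0.5 = 19.04, df 4 and 276, power 0.952.
- N = 138: power 0.947.

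So 141 is the smallest total in equal groups that reaches .95, and the figure is reproduced. Other inputs also give 141: ρ = 0.6 with ε = 0.75 (0.954), ρ = 0.7 with ε = 0.5 (0.951), and the time main effect at ρ = 0.4 (0.953). With ε = 1, the interaction needs 195 at ρ = 0.3 and 87 at ρ = 0.7. The stated inputs therefore do not identify the calculation.

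**3. The d to r² step.** r² = d²/(d² + 4) = 1/5 = .20, and f = √(.20/.80) = 0.5. The same interaction test then has power 0.948 at N = 15 and 0.982 at N = 18. About 18 participants would be enough, so this step does not lead to 141.

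**4. What f = .15 means in SD.** Assume both low-vision groups improve by the same amount at 6 months and hold it, while controls do not change. A 1 SD step then gives an interaction f of 0.222 with equal groups and 0.204 with a 75/75/50 split. Hence f = .15 corresponds to 0.15/0.222 = 0.675 SD or 0.15/0.204 = 0.735 SD. The step pattern and the split of the 150 patients are assumptions.

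**5. Detectable difference, low vision versus control.** With 10% loss per visit (Sample Size), 150 and 50 become 135 and 45 at 6 months, and 121 and 40 at 12 months (150 × 0.81 = 121.5; 50 × 0.81 = 40.5, rounded down). In SD units:

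- single visit minus baseline: se = √[2(1 − ρ)(1/n₁ + 1/n₂)]
- mean of both visits minus baseline: se = √[1.5(1 − ρ)(1/n₁ + 1/n₂)]

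The detectable difference at 95% power is (1.960 + 1.645) × se.

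| Contrast | se, ρ = 0.5 | Detectable | se, ρ = 0.7 | Detectable |
|---|---|---|---|---|
| 6 months (135/45) | 0.172 | 0.62 SD | 0.133 | 0.48 SD |
| 12 months (121/40) | 0.182 | 0.66 SD | 0.141 | 0.51 SD |
| Mean of both (121/40) | 0.158 | 0.57 SD | 0.122 | 0.44 SD |

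These use available cases. A mixed model that uses partial data does slightly better.

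**6. Patients as their own comparison.** With 121 completers, a true change of 0.2 SD and a two-sided 0.05 test:

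- mean of both visits: se = √[1.5(1 − ρ)/121] = 0.079 (ρ = 0.5) or 0.061 (ρ = 0.7); power about 72% or 91%
- single visit: se = √[2(1 − ρ)/121] = 0.091 or 0.070; power about 59% or 81%

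This comparison does not remove practice effects from repeated testing.

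**The case against.** Three arguments have weight.

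*The design points to f and the interaction.* Naming a within-between ANOVA in that software makes Cohen's f for the interaction the likeliest reading, and calling .15 small can be defended on the f scale. This stands. A reader might infer that 141 is miscalculated; the reproduction shows it is not. What remains is that the tested effect, correlation and epsilon cannot be recovered from the text.

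*The plan already has safeguards.* Confidence intervals and Bayes Factors help in interpreting a null result, and Study Design commits the whole design and analysis to a stage 1 pre-registered report. Neither is an error-control rule, and the protocol supplies none of the missing items. The report is not among the documents, so it may settle them; it is the natural place to do so.

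*The study is not shown to be insensitive.* A reader might infer that it would usually miss small cognitive effects. Under the step pattern, with 162 completers (200 × 0.81), the 4-df interaction test has 14% power at 0.2 SD for correlation 0.5 and 22% for 0.7. But other assumed patterns, splits and the same two correlations move this between 8% and 64%, and the documents give none of these inputs. Within-patient power is much higher, and any precision gained from the planned covariates is not counted. The documents do not support a general statement about power, and 162 expected completers exceed the 141 required.

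The choice of primary score and of Holm or FDR belongs to the investigators. That some choice is needed is not a matter of taste.

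**Conclusion.** The main point holds. As written, the cognitive question is tested on four or five outcomes with no primary and no error control. The chance of at least one false positive is about 16% to 18% if the tests are correlated 0.5 and 18.5% to 22.6% if independent, for one test per outcome. Hypotheses and the functional analysis section also disagree on whether the improver comparison is confirmatory. No power is given here for that comparison, because the documents provide neither a definition of improvement nor an expected split. This should be fixed before outcomes are seen.

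The second point is a reporting gap, not an arithmetic error. The 141 is correct under the most natural inputs, but those inputs are unstated and the d to r² step plays no part in it. On the SD scale, f = .15 is about 0.7 under the assumed step pattern, so the sensitivity statement should not be read as a difference of 0.15 SD. The SD figures rest on assumed correlations of 0.5 and 0.7 and on the plan's own attrition rate.

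**What to change.** Keep n = 200. In the stage 1 report, before outcomes are seen:

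1. Name one primary cognitive score. A memory score fits the opening research question, which puts memory in brackets after cognitive functioning.
2. Name one primary contrast, at a time point consistent with Hypotheses: benefit at 6 months, maintained at 12.
3. Apply Holm or FDR to the remaining cognitive tests, and say whether the MoCA is an outcome or a descriptor.
4. Reconcile Hypotheses with the functional analysis section on the improver versus non-improver comparison. If it is a hypothesis test, define improvement in advance; if exploratory, say so in both places.

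In Sample Size, state the metric, tested effect, correlation and epsilon behind 141, and drop the d to r² step or say that it is background only. Replace the .15 with the detectable difference for the chosen contrast, for example: *With 95% power, a low-vision versus control difference in change at 6 months of about 0.62 SD (correlation 0.5) or 0.48 SD (correlation 0.7), in available cases after 10% loss.* Use the 12-month or two-visit figures above if that contrast is chosen. If within-patient power is quoted, give it at both correlations, name the visit, and note the practice effects.

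The cost is no extra patients or visits. The other cognitive tests become secondary, and the stated sensitivity will look less favourable.
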